6.0 Study Endpoints

6.1 The primary endpoints in the proposed study are: 1) the level of cognitive functioning (as measured by the neuropsychological tests and self-reported cognitive functioning using the PAOFLI)

Secondary endpoints are: 1) Circadian activity rhythms using an actigraph (a small device similar in size to a watch that measures sleep and wake activity); 2) The Pittsburgh Sleep Quality Index; 3) the FACIT Fatigue Scale; 4) Quality of Life measured by the SF-36 scale; 5) a Credibility/Expectancy Questionnaire; 6) levels of Inflammatory Immune Markers; 7) the amount of time that the light boxes are used; 8) treatment satisfaction using the FACIT-TS-G scale; 9) depressed mood as measured by the CES-D; and 10) neurobehavioral functioning as measured by the Frontal Systems Behavior Scale.

6.2 With regard to safety endpoints, there are no known risks associated with the use of the light boxes in the treatment of cognitive impairments. However, we will monitor those who decide to cease treatment because they find the treatment approach unacceptable along with their concerns regarding treatment.

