9.0 Data and Specimen Management

9.1 Data analysis plan

Descriptive statistics will be calculated for the entire group and separately for each treatment group. T-tests and Fisher's exact tests will be used to assess group differences at baseline for possible confounders (i.e., demographic variables, and clinical characteristics *including time since transplant*). Variables showing differences between the two groups will be used as covariates in subsequent analyses. Since there is no known seasonality effect on cognitive functioning, seasonality will not be controlled in these analyses.

Aim 1: Assess the feasibility and acceptability of BWL as an intervention for CRCI in HSCT survivors. Feasibility: We will adhere to currently accepted practice for feasibility studies¹¹⁰ by measuring the number of eligible patients, willingness of participants to be randomized, follow-up rates, the number who cease the intervention and their specific concerns about the intervention. We will monitor adherence by examining integrated meter data (i.e., time and duration of light box use). We expect high adherence, but if there is variation in duration, we will use duration as a predictor of the outcomes. Participants will be asked to log light box use (beginning and ending time) and reasons for not using it if that occurs. There is no gold standard for what constitutes a “feasible” study and relevant CRCI intervention feasibility studies have not been home-based.^{18, 111} Nevertheless, in an inpatient cognitive rehabilitation study of HSCT patients, 78% completed baseline, intervention, and time 2 assessments.¹⁸ A light exposure feasibility study for seasonal affective disorder deemed a 68% completion rate as acceptable,¹¹² and this is the criteria we will use in this study. In [name]'s pilot study, breast cancer

PROTOCOL TITLE: Treating cognitive impairments in cancer patients via systematic light exposure

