patients used the light box about 50% of the required days. This usage frequency was sufficient for cognitive improvement to occur in the BWL group. A 50% level of adherence will be considered acceptable in this study. Acceptability: As recommended in the literature, in addition to accrual rates, we will assess acceptability by evaluating participants' comments about the intervention after they have had experience with it.¹¹³ Finally, a comparison of the BWL and DRL on the FACIT-TS-G will be conducted using t-tests. Significant differences in favor of the BWL condition are expected.

Aim 2: Examine whether BWL compared with DRL among HSCT survivors suffering from cognitive impairment yields significant improvements in cognitive functioning. We will examine the cognitive functioning subscales and composite scores in separate analyses. Linear mixed model analysis with repeated measures will be conducted using the SAS procedure MIXED.

Contrasts will compare groups across assessments. The linear mixed model approach has a range of choices for the error variance/covariance structure and accommodates missing data thus protecting against a "completers only" bias. Since multiple outcomes will be correlated with one another, *p*-values for significance will be Sidak-adjusted for multiple comparisons. If there is variation in light box utilization, we will use duration time as a predictor of the outcome measures as in Aim 1. No pre-intervention bias favoring BWL over DRL is anticipated. However, we will test this assumption by crossing expectancy with the treatment condition. This interaction is not expected to be significant. These results will determine preliminary efficacy and sustainability of the intervention.

Power: Based on [name]'s pilot study with 10 breast cancer patients, the effect size indicated that we would need a sample size of 19 to achieve power at 0.80. However, the sample size is likely too small to provide reliable estimates of improvement in cognitive functioning. One of the main aims is to determine preliminary efficacy of the intervention in preparation for a larger scale trial. For a total sample of 80, we calculated the mean difference between the two treatment arms for the Neurocognitive (composite) Index and assumed a repeated measures design with an autoregressive lag 1 error structure and autocorrelation of 0.60. The difference able to be detected with power equal to 0.80 and alpha = 0.05, is 0.209.

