Aim 3: Examine whether BWL compared with DRL affects sleep and psychological variables (depressed mood, fatigue) which have been implicated as correlates of cognitive functioning in cancer patients. Hypothesis 2: Sleep quality and psychological variables will improve in the BWL group compared to the DRL group. The Aim 1 analytic strategy will be used in the analysis of this aim. Power: Our preliminary R-21 study that examined BWL vs. DRL on cancer-related fatigue in a mixed cancer population (including HSCT) provided guidance for the power. Sleep Quality: While survivors in the BWL group had better sleep quality scores than the DRL group, the main effect for treatment was not statistically significant, no doubt due to sample size. Cohen's *d* was 0.63. For a repeated measures design with alpha equal to 0.05 and a sample size of 40 per group, power=0.99. CAR: There was significant time x treatment interaction (*p*=0.02) on the F statistic. We calculated power for a repeated measures design with autoregressive lag 1 structure and autocorrelation of 0.60. With alpha equal to 0.05 and sample size of 40 per group, power=0.99. Fatigue: As with CAR, there was significant time x treatment interaction (*p*=0.003). Using the same method as above, power = 0.99. Depressed mood: There was a significant (*p*=0.004) time x treatment interaction. Using the same method as above, power = 0.99.

Exploratory Aims: Explore a) whether BWL compared with DRL affects biological (inflammatory immune response) variables; and b) whether the effects of BWL compared to

PROTOCOL TITLE: Treating cognitive impairments in cancer patients via systematic light exposure

DRL on cognitive functioning are mediated by sleep, chronobiological factors (i.e., circadian activity rhythms), biological factors (i.e., inflammatory immune response), and psychological factors (i.e., fatigue, depressed mood).

- a) Assess whether the BWL intervention affects biological factors (IL-1ra, IL-6, IL-8, IL-10, sTNF-III, CRP, PBMCs, and intracellular RNA) that have been identified as correlates of CRCI. Biological variables will be measured at Times 1 and 2. The mixed linear model approach described in Aim 2 will be used here.

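### The expectancy-by-treatment interaction in Aim 2 cannot test whether expectancy favoured BWL, which is the assumption it is meant to check

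*Combined protocol and SAP*

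**What the plan says.** Three consecutive sentences in Section 9.1, Aim 2, set out the check. The assumption is "No pre-intervention bias favoring BWL over DRL is anticipated". The method is "we will test this assumption by crossing expectancy with the treatment condition". The expected result is "This interaction is not expected to be significant". They stand in the paragraph that describes the linear mixed model for cognitive outcomes. Bias is not defined.

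The rest of the plan treats expectancy as follows:

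- Section 6.1 lists "a Credibility/Expectancy Questionnaire" among the secondary endpoints. Section 7.3, item 15, collects it at Times 1, 3 and 4.
- Section 9.1 opens with descriptive statistics by arm. It adds that t-tests and Fisher's exact tests "will be used to assess group differences at baseline for possible confounders", but names only demographic variables and clinical characteristics.
- The Aim 3 paragraph covers sleep, circadian rhythm, fatigue and depressed mood, not expectancy.

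No section plans a contrast of expectancy between arms.

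**The concern.** The assumption concerns level and direction: participants should not hold a more favourable belief about BWL than about DRL. The test targets a different parameter, the between-arm difference in how strongly expectancy predicts outcome. The two can disagree in both directions. A large expectancy gap with equal slopes leaves the interaction null. Equal expectancy with unequal slopes can make it significant.

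Read as the plan intends, a null interaction would be reported as support for the assumption. This matters most for one of the two primary components, "self-reported cognitive functioning using the PAOFLI". The lamps differ in output (about 1000 lux against less than 50, Section 7.1.1), and this is the only expectancy analysis the plan names. Aim 2 is also meant to inform a larger trial.

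**Working it through.** The plan gives no figure for this test, so there is none to reproduce.

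**Inputs from the documents**
- 40 per arm (Sections 9.1 and 9.2).
- Alpha 0.05, with sidedness not stated; two-sided is assumed here.
- AR(1) autocorrelation 0.60 (Section 9.1, Aim 2 power).
- Neuropsychological testing at Times 1, 3 and 4 (Section 7.3, item 6).
- For a reduced-data case, the feasibility criterion from a light study that "deemed a 68% completion rate as acceptable": 0.68 × 40 = 27.2, taken as 27 per arm.

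**Assumed, because the documents give nothing**
- Expectancy gap δ between arms from 0 to 1.0 SD.
- Common slopes of 0.1, 0.3 and 0.4, or unequal slopes of 0.3 against 0 and 0.5 against 0.

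**Step 1. What the term estimates.** Write the outcome as Y = a + τA + βE + γAE + error, with A the arm (1 for BWL) and E expectancy. Then γ is the BWL slope minus the DRL slope. Each slope is fitted within its own arm, so adding a constant to every BWL participant's E changes neither slope, and γ does not contain δ. With γ = 0 and no light effect, the bias in the unadjusted arm difference is β × δ, for example 0.4 × 0.5 = 0.20 SD. The interaction does not respond to this quantity.

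**Step 2. Gap present, equal slopes.** The simulation used 5,000 trials per cell, residual SD 1, no light effect, and expectancy acting on Times 3 and 4. GLS was fitted with arm, expectancy and their product at each time. The interaction was tested both as the average over Times 3 and 4 and as change from Time 1. Over 3 slopes × 5 gaps (0, 0.25, 0.5, 0.75, 1.0 SD) × 2 completeness settings × 2 versions = 60 results, the rejection rate was 0.041 to 0.056 throughout. A single-outcome simulation of 10,000 runs shows what goes unseen:
- δ = 0.5, slope 0.4: spurious arm effect 0.20 SD; interaction significant in 4.8% of runs.
- δ = 1.0, slope 0.5: spurious effect 0.50 SD, falsely significant in 60% of runs; interaction significant in 5.1%.

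**Step 3. No gap, unequal slopes.** Rejection rates from the repeated-measures simulation:

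| Slopes | Complete data | 27 per arm at Times 3 and 4 |
|---|---|---|
| 0.3 vs 0 | 29-30% | 23-24% |
| 0.5 vs 0 | 65-67% | 51-53% |

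Repeat runs on complete data with other random numbers gave 28-32% and 65-68%.

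**Step 4. Weak even for its own question.** The slope difference detectable with 80% power (single outcome, residual SD 1) is about (1.96 + 0.84) × √(2/40) = 0.63 outcome SD per SD of expectancy.

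**Step 5. The direct comparison.** Power of a two-sample t-test on expectancy:

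| Gap (SD) | 40 per arm | 27 per arm |
|---|---|---|
| 0.25 | 20% | 15% |
| 0.5 | 60% | 44% |
| 0.75 | 91% | 77% |
| 1.0 | 99% | 95% |

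The 95% CI half-width is t(0.975, 78) × √(2/40) = 0.445 SD at 40 per arm and t(0.975, 52) × √(2/27) = 0.546 SD at 27. A non-significant t-test alone would therefore also be weak evidence, and the interval must be shown.

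**Step 6. Timing.** If the Time 1 form is completed before the lamp is seen, any arm gap is chance. Its SD is √(2/40) = 0.224, and it exceeds 0.5 SD in about 2.5% of trials. The power figures for larger gaps then apply to later forms. Adjusting for Time 1 expectancy does not remove belief formed afterwards: with slope 0.3 and a gap of 0.5 SD arising after Time 1, the arm difference is 0.3 × 0.5 = 0.15 both unadjusted and adjusted.

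**The case against.** Bias is undefined. If it means that the treatment effect should not depend on prior belief, the interaction does address it. This stands as a possible reading, but a bias favouring one arm is not a natural description of effect modification, and the plan would need to say so. That the interaction sits in the outcome model is inferred from its place in the Aim 2 text. However, a plain comparison of expectancy between arms contains no expectancy-by-treatment interaction.

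The stronger objection is timing. Section 7.1.1 puts baseline a week before the intervention, allows questionnaires at home before the visit, and starts light use after Time 1. Section 20.1 mentions baseline before randomisation. On the likelier reading a Time 1 gap is chance, so a direct Time 1 comparison checks only randomisation, and adjusting for it does not remove later expectancy. A Time 3 difference may reflect real benefit. All of this stands. It limits what any expectancy check can show here, but it does not make the interaction a test of the stated assumption.

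It is also fair that the equal-slope simulations show only test size (Step 1 already proves the point), that every gap and slope is assumed, and that 68% is a feasibility threshold and not a projected dropout rate. By-arm descriptives, if they include expectancy, would nearly supply the missing contrast. No decision or primary estimate depends on this check.

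**Conclusion.** The concern holds. Read as a statement about the level of expectancy, the assumption is not tested by the named analysis: the interaction's rejection rate stays near 5% whatever the gap, and it can reach about two thirds with no gap at all. The algebra needs no assumed values. The rejection rates rest on the illustrative slopes, normal errors and AR(1) 0.60 treated as known. If effect modification was meant, the test fits but the wording does not.

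The consequence is moderate. The main treatment contrast is unaffected, participants are told that two wavelengths are being tested, and the other primary component is a standardised test battery. The correction should still be made, because a null interaction would otherwise be reported as reassurance that it cannot give.

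**What to change.** In Section 9.1, Aim 2:

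1. Replace the stated test with the BWL minus DRL difference in Credibility/Expectancy score, with its 95% CI, at Time 1. Report the same at Time 3 as descriptive, since it may reflect benefit.
2. As a sensitivity analysis, report the Aim 2 arm effect with and without Time 1 expectancy as a main effect.
3. Keep the interaction, with expectancy centred, only as exploratory effect modification. Delete the statement that it tests for bias.
4. State whether the Time 1 form is completed before the assigned lamp is seen. If so, say that a Time 1 difference is chance only, that adjusting for it cannot remove expectancy formed later, and that the Time 1 check does not rule out expectancy bias in the arm comparison.

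Optionally, for participants still to be enrolled, repeat the form once after the lamp is shown and before first use.

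Items 1 to 4 need SAP wording and a small amount of analysis on data already collected at Times 1, 3 and 4. The optional repeat costs one short form per participant.

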4.0 Study-Wide Number of Subjects

Eighty autologous and allogeneic HSCT survivors will be recruited at Northwestern University, Feinberg School of Medicine, Department of Medical Social Sciences from Northwestern Memorial Hospital (NMH) and Robert H. Lurie Comprehensive Cancer Center (RHLCCC).

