9.2 Power analyses

Aim 1 Power: Based on [name]'s pilot study with 10 breast cancer patients, the effect size indicated that we would need a sample size of 19 to achieve power at 0.80. However, the sample size is likely too small to provide reliable estimates of improvement in cognitive functioning. One of the main aims is to determine preliminary efficacy of the intervention in preparation for a larger scale trial. For a total sample of 80, we calculated the mean difference between the two treatment arms for the Neurocognitive (composite) Index and assumed a repeated measures design with an autoregressive lag 1 error structure and autocorrelation of 0.60. The difference able to be detected with power equal to 0.80 and alpha = 0.05, is 0.209.

Aim 2 Power: Our preliminary R-21 study that examined BWL vs. DRL on cancer-related fatigue in a mixed cancer population (including HSCT) provided guidance for the power. Sleep Quality: While survivors in the BWL group had better sleep quality scores than the DRL group, the main effect for treatment was not statistically significant, no doubt due to sample size. Cohen's d was 0.63. For a repeated measures design with alpha equal to 0.05 and a sample size of 40 per group, power=0.99. CAR: There was significant time x treatment interaction (p=0.02) on the F statistic. We calculated power for a repeated measures design with autoregressive lag 1 structure and autocorrelation of 0.60. With alpha equal to 0.05 and sample size of 40 per group, power=0.99. Fatigue: As with CAR, there was significant time x treatment interaction (p=0.003). Using the same method as above, power = 0.99. Depressed mood: There was a significant (p=0.004) time x treatment interaction. Using the same method as above, power = 0.99.

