20.0 Number of Subjects

20.1 Total number of subjects to be accrued

We expect to recruit 80 study participants whom we will draw from the pool of auto-HSCT and allo-HSCT survivors at Northwestern. Northwestern undertakes approximately 180 autologous HSCTs annually. Based on these numbers, we expect to be able to approach the necessary 227 HSCT patients between 1 and 5 years post-transplant across 48 months of recruitment. Research that examined HSCT survivors in our earlier BWL research suggests that 11.9% of those eligible will refuse to undertake the screening leaving 200 patients who will participate in the screening assessment. Research suggests that more than 40% of those individuals (the most conservative estimate) will meet criteria for entry into the study, leaving 80 interested participants eligible to complete the baseline assessment and randomization into the study.

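### The detectable difference of 0.209 and the 0.99 powers make no allowance for loss after randomisation, although exactly 80 are randomised and 68% completion is accepted (minor)

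*Combined protocol and SAP*

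**What the plan says.** Section 9.1 (Aim 2 Power) states: "For a total sample of 80, we calculated the mean difference between the two treatment arms for the Neurocognitive (composite) Index". It assumes a first-order autoregressive error structure with autocorrelation 0.60. Section 9.2 repeats the result: "The difference able to be detected with power equal to 0.80 and alpha = 0.05, is 0.209". For the circadian outcome section 9.1 adds: "With alpha equal to 0.05 and sample size of 40 per group, power=0.99". Sleep quality also uses 40 per group, and fatigue and depressed mood are powered by the same method, all with a result of 0.99.

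The number enrolled is the same 80. Section 4.0 states: "Eighty autologous and allogeneic HSCT survivors will be recruited". Section 20.1 shows where they are counted: 227 approached, 200 screened, "leaving 80 interested participants eligible to complete the baseline assessment and randomization into the study".

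Under Aim 1, section 9.1 notes that a light study in seasonal affective disorder "deemed a 68% completion rate as acceptable" and adds: "this is the criteria we will use in this study". It also cites 78% completion in an inpatient cognitive rehabilitation study of transplant patients. The only provision for loss is the likelihood-based mixed model, which accepts partial records. No dropout rate, inflation factor or reduced-N power is given.

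**The concern.** The N behind the power figures equals the N randomised, so nothing is held back for participants who leave. That these figures assume complete data is an inference from the absence of any attrition term; the documents do not say so.

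The neuropsychological battery is given at Times 1, 3 and 4 only (section 7.3), and Time 2 is questionnaires. A participant lost during the four-week intervention therefore has baseline cognitive data only and adds little or nothing to the comparison of arms.

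Aim 2 is meant to supply preliminary efficacy for a larger trial, and section 9.1 also looks to sustainability, which rests on Time 4. Someone who reads 0.209 at face value would take a null result to exclude smaller effects than the data could support.

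**Working it through.** **Inputs.** N = 80, 40 per arm; power 0.80; alpha 0.05 (two-sided assumed, as sidedness is not stated); AR(1) correlation 0.60; difference 0.209; completion 68% (accepted) and 78% (cited), all from section 9.1. Cognitive visits at Times 1, 3 and 4, from section 7.3.

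**1. Where 80 is counted.** 227 × (1 − 0.119) = 200; 200 × 0.40 = 80. This is before any post-randomisation loss.

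**2. The plan's own figure.** Detectable difference = (1.96 + 0.84) × SD × √(2/40 × v), where v is the variance of the contrast in units of SD². With SD = 1:
- one visit, v = 1: 0.626
- mean of three visits, v = (3 + 2(0.6 + 0.6 + 0.36))/9 = 0.68: 0.517

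Other natural two-sided contrasts give 0.48 to 0.78, and slopes 0.26 to 0.35. None gives 0.209, which for a mean of three visits would imply an SD of 0.209/0.517 = 0.40. Since the SD, visits and contrast are not stated, 0.209 can be neither reproduced nor refuted.

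**3. Scaling for loss.** The SD cancels when only the ratio of standard errors is used:
- detectable difference = 0.209 × ratio
- power at 0.209 = Φ(2.80/ratio − 1.96)

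*Complete cases only*, ratio = 1/√(completion):
- 78%: 0.209/√0.78 = 0.237, power 0.70
- 68%: 0.209/√0.68 = 0.253, power 0.64

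*Planned mixed model*, keeping partial records. Example: Time 3 minus Time 1, with 32% lost after Time 1. With full data the variance is 2(1 − 0.6) = 0.80. With loss it is (1 − 0.36)/0.68 + (1 − 0.6)² = 1.101. Ratio = √(1.101/0.80) = 1.173, giving 0.245 and power 0.67. If the baseline means are constrained equal, the ratio is √[(0.64/0.68)/0.64] = 1.213, the same as complete cases.

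The same method at 68% completion gives (detectable difference, with power at 0.209 in brackets):

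| Contrast | All loss after Time 1 | Half after Time 1, half after Time 3 | All loss after Time 3 |
|---|---|---|---|
| Mean of three visits | 0.227 (0.73) | 0.219 (0.76) | 0.214 (0.78) |
| Time 3 − Time 1 | 0.245 (0.67) | 0.224 (0.74) | 0.209 (0.80) |
| Time 4 − Time 1 | 0.240 (0.68) | 0.235 (0.70) | 0.232 (0.71) |
| Time 3, common baseline | 0.253 (0.64) | 0.228 (0.73) | 0.209 (0.80) |
| Time 4, common baseline | 0.253 (0.64) | 0.247 (0.66) | 0.242 (0.68) |

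At 78% the range is 0.209 to 0.237, with power 0.80 to 0.70.

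**4. Secondary powers.** Taking 0.99 as exact, complete-case scaling at 68% gives Φ((2.326 + 1.960) × √0.68 − 1.960) = 0.94. Sleep quality, fatigue and mood are also collected at Time 2, so an early leaver can still contribute post-baseline data. For these outcomes complete-case scaling is therefore a pessimistic bound.

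**5. Against the pilot effect.** If 0.209 and the pilot's 0.33 SD (section 2.2) share a scale, which is an assumption, power for 0.33 at 68% completion is Φ(0.33/0.209 × 2.80 × √0.68 − 1.96) = 0.95.

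**The case against.** The strongest reply is that the plan already deals with missing data. The mixed model keeps partial records, so complete-case figures overstate the damage. This stands in part: the table shows the model recovering some of the loss, and all of it for a Time 3 contrast when every loss comes after Time 3. A reader might infer that 0.209 holds only with no loss at all, or that 0.24 to 0.25 is what the design will deliver. Neither follows. Values near 0.25 need non-completers with no post-baseline cognitive data, or nearly all loss bearing on a Time 4 comparison.

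Second, 68% is a feasibility pass mark, not a prediction, and completion is not defined visit by visit. The 78% comes from an inpatient study, whereas this intervention is home-based. Section 2.2 reports that the 10 patients in the breast cancer light pilot were able to complete all assessments. All of this stands, so 68% to 78% should be read as a planning range that the plan itself tolerates.

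Third, a reader might take every sample-size statement to be affected. The pilot-based figure of 19 does not rest on 80 and is untouched.

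Fourth, the consequence is small: this is a feasibility and preliminary-efficacy study, and the plan states no go/no-go rule that turns on a null result. That stands and sets the severity. It does not remove the omission, because a mixed model limits completers-only bias without restoring the information in 80 full records.

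**Conclusion.** The concern holds as a minor point. The 0.209 and the 0.99 powers are stated without any allowance for loss, in a design that randomises exactly the number they use and accepts 68% completion. At that floor the detectable difference could be up to about 21% larger (0.253 against 0.209), and at 78% up to about 13% larger (0.237). With loss that falls late it may hardly change.

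These figures assume a two-sided 5% test, AR(1) correlation of 0.60, three cognitive visits, equal loss in the two arms, and loss that the mixed model can treat as ignorable. They measure the sensitivity of 0.209 to loss and do not validate 0.209 itself. A reader might also infer that the trial is underpowered or needs a larger sample. The documents do not support that: the stated aim is preliminary, and on the shared-scale assumption power for the pilot effect stays near 0.95. What is misstated is how small a difference the trial could detect.

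**What to change.** Keep 80. In sections 9.1 and 9.2:

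1. State the SD, the visits and the contrast behind 0.209, and whether the test is two-sided.
2. Add a sentence such as: *The figure of 0.209 assumes no loss; with 68% to 78% completing, the detectable difference at 0.80 power is up to about 0.24 to 0.25, depending on the timing of loss.* Once item 1 is settled, replace this range with the value for the chosen contrast.
3. Recompute the sleep, circadian, fatigue and mood powers with loss allowed for, under the planned mixed model and each outcome's own visit schedule. Completer counts alone would be wrong for outcomes also measured at Time 2.
4. Define completion by visit, so that the feasibility criterion and the power statement refer to the same thing.

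The cost is a few sentences and a short recalculation, and the stated figures become slightly less favourable. No participants are added. Recruiting for 80 completers would instead need 80/0.68 = 118 (or 80/0.78 = 103), which the stated aims do not require.
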